11.4.2 Biochemical Abnormalities

Table 11.4.2.1 Biochemical abnormalities: Worst grade per treatment

	BOS+LRB						LRB alone					
	All grades		Gr ≥ 3		Gr ≥ 4		All grades		Gr ≥ 3		Gr ≥ 4	
	N	%	N	%	N	%	N	%	N	%	N	%
ALT increase												
AST increase												
...*												

Notes: Percentage is based on number of patients by treatment, when applicable.

*Creatinine increased, hyperglycemia, hypoglycemia, CPK increased, GGT increased, bilirubin increased, hypoalbuminemia, hypernatremia, hyponatremia, hyperkalemia, hypokalemia, hypermagnesemia, hypomagnesemia, hypercalcemia, hypocalcemia.

BOS, bosentan; LRB, lubinectedin.

Listing 11.4.2.2 Biochemical abnormalities grade ≥ 3

Treatment group [†]	Subject	Event	Grade

[†]BOS+LRB/LRB alone

Listing 11.4.2.3 Biochemical tests not assessed

Treatment group [†]	Subject	Lab. test

[†]BOS+LRB/LRB alone

Table 11.4.2.4 Biochemical abnormalities: Worst grade per patient

	S1 (TR)						S2 (RT)						Total							
	All grades		Gr ≥ 3		Gr ≥ 4		All grades		Gr ≥ 3		Gr ≥ 4		All grades		Gr ≥ 3		Gr ≥ 4			
	N	%	N	%	N	%	N	%	N	%	N	%	N	%	N	%	N	%	N	%
ALT increase																				
AST increase																				
...*																				

Notes: Percentage is based on number of patients in total and by sequence, when applicable.

*Creatinine increased, hyperglycemia, hypoglycemia, CPK increased, GGT increased, bilirubin increased, hypoalbuminemia, hypernatremia, hyponatremia, hyperkalemia, hypokalemia, hypermagnesemia, hypomagnesemia, hypercalcemia, hypocalcemia

S1, Sequence 1; S2, Sequence 2; TR, test-reference; RT, reference-test.

Listing 11.4.2.5 Biochemical abnormalities by cycle grade ≥ 3

Sequence	Subject	Event	Cycle	Grade

Listing 11.4.2.6 Biochemical tests not assessed by cycle

Sequence	Subject	Cycle	Lab. test

11.4.3 Laboratory Values Over Treatment

Table 11.4.3.1 Shift of hematological abnormalities, worst grade per patient vs. baseline

Baseline grade	Worst grade per patient during treatment									
	Grade 1		Grade 2		Grade 3		Grade 4		Grade 5	
	N	%	N	%	N	%	N	%	N	%
S1 (TR)										
Anemia	Grade 0									
	...									
	Grade 4									
Leukopenia	Grade 0									
	...									
	Grade 4									
...	Grade 0									
	...									
	Grade 4									
S2 (RT)										
Anemia	Grade 0									
	...									
	Grade 4									
Leukopenia	Grade 0									
	...									
	Grade 4									
...	Grade 0									
	...									
	Grade 4									
Total										
Anemia	Grade 0									
	...									
	Grade 4									
Leukopenia	Grade 0									
	...									
	Grade 4									
...	Grade 0									
	...									
	Grade 4									

Notes: Percentage is based on number of patients in total and by sequence, when applicable.

*Lymphopenia, Neutropenia and Thrombocytopenia.

S1, Sequence 1; S2, Sequence 2; TR, test-reference; RT, reference-test.

If a low number of patients with grade ≥ 3 neutropenia or thrombocytopenia, the following table will be omitted and the information will be provided in a listing.

Table 11.4.3.2 Time course for neutrophils and platelets

	BOS+LRB		LRB alone		Total	
	N	Median (range)	N	Median (range)	N	Median (range)
Neutropenia (Grade≥ 3)						
Onset day						
Nadir day						
Recovery day						
Days of recovery to grade ≤ 2						
Thrombocytopenia (Grade≥ 3)						
Onset day						
Nadir day						
Recovery day						
Days of recovery to grade ≤ 2						

BOS, bosentan; LRB, lirbinezidin.

Table 11.4.3.3 Shift of biochemical abnormalities, worst grade per patient vs baseline

Baseline grade	Worst grade [†] per patient during treatment									
	Grade 1		Grade 2		Grade 3		Grade 4		Grade 5	
	N	%	N	%	N	%	N	%	N	%
S1 (TR)										
ALT increase	Grade 0									
	...									
	Grade 4									
AST increase	Grade 0									
	...									
	Grade 4									
...	Grade 0									
	...									
	Grade 4									
S2 (RT)										
ALT increase	Grade 0									
	...									
	Grade 4									
AST increase	Grade 0									
	...									
	Grade 4									
...	Grade 0									
	...									
	Grade 4									
Total										
ALT increase	Grade 0									
	...									
	Grade 4									
AST increase	Grade 0									
	...									
	Grade 4									
...	Grade 0									
	...									
	Grade 4									

Notes: Percentage is based on number of patients in total and by sequence, when applicable.

[†]For ALT, AST, AP, GGT, and Bilirubin parameters, worst grade will be calculated compared to baseline.

*Creatinine increased, hyperglycemia, hypoglycemia, CPK increased, GGT increased, bilirubin increased, hypoalbuminemia, hypernatremia, hyponatremia, hyperkalemia, hypokalemia, hypermagnesemia, hypomagnesemia, hypercalcemia, hypocalcemia.

S1, Sequence 1; S2, Sequence 2; TR, test-reference; RT, reference-test.

If a low number of patients with grade ≥ 3 ALT or AST increased, the following table will be omitted and the information will be provided in a listing.

Table 11.4.3.4 Time course for AST and ALT

	BOS+LRB		LRB alone		Total	
	N	Median (range)	N	Median (range)	N	Median (range)
AST (Grade≥ 3)						
Onset day						
Peak day						
Recovery day						
Days of recovery to grade ≤ 2						
ALT (Grade≥ 3)						
Onset day						
Peak day						
Recovery day						
Days of recovery to grade ≤ 2						

BOS, bosentan; LRB, lubirenedin.

If appropriate, inter-cycle time courses for neutropenia, thrombocytopenia or any other significant parameter will be displayed in graphs.

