6 STATISTICAL METHODOLOGY

The PK definitions and analysis plan will be described by the Clinical Pharmacology department in a separate document. The present Statistical Analysis Plan (SAP) is focused on the statistical methodology for safety.

Safety analyses will consider treatment emergent AEs and SAEs, according to their relationship with study treatment, as well as analytical results, deaths and the reasons for treatment discontinuations, delays and/or dose reductions.

All AEs and SAEs will be coded using the Medical Dictionary for Regulatory Activities (MedDRA).

Descriptive statistics will be used to characterize the profiles of drug-related AEs, drug-related deaths, SAEs, clinical laboratory data, drug-related delays and/or treatment discontinuations. Tables will be displayed by sequence and treatment (Sequence 1 [TR] vs. Sequence 2 [RT]) and treatment group (Test [lurbinectedin administered in combination with bosentan] vs. Reference [lurbinectedin alone]) .

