11.4 Clinical Laboratory Evaluation

11.4.1 Hematological Abnormalities

Table 11.4.1.1 Hematological abnormalities: Worst grade per treatment

	BOS+LRB						LRB alone					
	All grades		Gr \geq 3		Gr \geq 4		All grades		Gr \geq 3		Gr \geq 4	
	N	%	N	%	N	%	N	%	N	%	N	%
Anemia												
Leukopenia												
Lymphopenia												
Neutropenia												
Thrombocytopenia												

Notes: Percentage is based on number of patients by treatment, when applicable.

BOS, bosentan; LRB, lirbinezidin.

Listing 11.4.1.2 Hematological abnormalities grade \geq 3

Treatment group [†]	Subject	Event	Grade

[†]BOS+LRB/LRB alone

Listing 11.4.1.3 Hematological tests not assessed by patient

Treatment group [†]	Subject	Lab. test

[†]BOS+LRB/LRB alone

Table 11.4.1.4 Hematological abnormalities: Worst grade per patient

	S1 (TR)			S2 (RT)			Total					
	All grades		Gr \geq 3	Gr \geq 4	All grades		Gr \geq 3	Gr \geq 4	All grades		Gr \geq 3	Gr \geq 4
	N	%	N	%	N	%	N	%	N	%	N	%
Anemia												
Leukopenia												
Lymphopenia												
Neutropenia												
Thrombocytopenia												

Notes: Percentage is based on number of patients in total and by sequence, when applicable.

S1, Sequence 1; S2, Sequence 2; TR, test-reference; RT, reference-test.

Listing 11.4.1.5 Hematological abnormalities by cycle grade \geq 3

Sequence	Subject	Event	Cycle	Grade

Listing 11.4.1.6 Hematological tests not assessed by cycle

Sequence	Subject	Cycle	Lab. test

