11.5 Linear Mixed-effects Model

If applicable, to compare the incidence of grade ≥ 4 or grade ≥ 3 between the combination and lurbinectedin alone, a generalized linear mixed-effects model will be fit to the data with treatment (Combination or lurbinectedin alone), period and sequence as fixed effects, and patients nested in sequences as a random effect.

Table 11.5.1.1 Safety comparison between combination and lurbinectedin alone[†]

	Combination	Lurbinectedin alone	p-value [‡]
Any grade ≥ 3 AE			
Any grade ≥ 4 AE			
Any grade ≥ 3 treatment-related AE			
Any grade ≥ 4 treatment-related AE			
Any abnormality (G ≥ 3) in laboratory value (hema, bio)			
Any abnormality (G ≥ 4) in laboratory value (hema, bio)			

[†] A generalized mixed-effects model will be fit for each safety evaluation

[‡] p-values will be provided for the comparison between treatments (combination vs. Lurbinectedin alone) or including the sequence effect if deemed necessary.

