Listing 13.13 Prior anticancer medical therapy

Sequence	Subject	None?	Regimen	Agent	Agent Coded	Agent Class	Setting	Start date	Stop date	Best response	PD date	Non PD
----------	---------	-------	---------	-------	-------------	-------------	---------	------------	-----------	---------------	---------	--------

Listing 13.14 Prophylactic medication

Sequence	Subject	Visit	Type	Medication	... [†]	Route	Daily dose	Units	Start date	Stop date	Time	Taken per protocol	Specify
----------	---------	-------	------	------------	------------------	-------	------------	-------	------------	-----------	------	--------------------	---------

(†) ATC1, ATC2, ATC3, ATC4

Listing 13.15 Lurbinectedin administration

Sequence	Subject	Visit	Date	Route	Start time	End time	Intended dose (mg/m ²)	Total intended dose (mg)	Total dose given	Total volume	BSA calculated for dose
----------	---------	-------	------	-------	------------	----------	------------------------------------	--------------------------	------------------	--------------	-------------------------

Listing 13.16 Lurbinectedin treatment modification

Sequence	Subject	Visit	Any modification	Treatment Modification	Reason	Adverse Event	Other, specify
----------	---------	-------	------------------	---------------------------	--------	---------------	----------------

Listing 13.17 Lurbinectedin re-administration

Sequence	Subject	Visit	Date	Not done?	Route	Total dose given	Start time	End time
----------	---------	-------	------	-----------	-------	------------------	------------	----------

Listing 13.18 Bosentan administration prior to lurtinectedin infusion

Sequence	Subject	Visit	Day	Date	Time	No. of capsules (125 mg)	Taken accordingly?	Reason	Contact	Reason if No contacted
----------	---------	-------	-----	------	------	-----------------------------	-----------------------	--------	---------	------------------------------

Listing 13.19 Hematological laboratory values

Sequence	Subject	Calc. cycle	Date	Hemoglobin (g/dl)	... [†]	WBC (x10 ⁹ /L)	Neutrophils (x10 ⁹ /L)	Lymphocytes (x10 ⁹ /L)	Platelets (x10 ⁹ /L)
----------	---------	-------------	------	-------------------	------------------	---------------------------	-----------------------------------	-----------------------------------	---------------------------------

(†) Hematocrit, RBC and monocytes.

Listing 13.20 Coagulation Test

Sequence	Subject	Visit	Calculated cycle	Date	Repeat	INR (ratio)

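### By-treatment myelosuppression outputs rest on grades or grade ≥3 cases: paired Day 8 and Day 15 counts are not compared, and the lurbinectedin-alone column is not limited to Cycles 1-2

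*SAP*

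**What the plan says.** SAP 4.1.2 makes the effect of bosentan on lurbinectedin's safety profile a secondary objective. For myelosuppression, the outputs split by treatment are these:

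- SAP 11.4.1, Table 11.4.1.1: "Hematological abnormalities: Worst grade per treatment". Listing 11.4.1.2 gives the grade ≥3 events.
- SAP 11.4.3, Table 11.4.3.2: "Time course for neutrophils and platelets". It gives onset, nadir and recovery days for grade ≥3 neutropenia and thrombocytopenia. If few patients qualify, "the following table will be omitted and the information will be provided in a listing".
- SAP 11.5, where applicable: "a generalized linear mixed-effects model will be fit to the data with treatment (Combination or lurbinectedin alone), period and sequence as fixed effects", with patient as a random effect. Its outcomes are the incidence of grade ≥3 or grade ≥4 events. Its laboratory rows combine hematology and biochemistry.

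The counts themselves appear as baseline summaries by sequence (Table 10.2.6.2) and in raw listings such as "Listing 13.19 Hematological laboratory values" (Appendix IV). There is also a conditional graph: "If appropriate, inter-cycle time courses for neutropenia, thrombocytopenia or any other significant parameter will be displayed in graphs". The shift table (11.4.3.1) is by sequence, not by treatment.

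SAP 6 and 7.6 define Reference as lurbinectedin alone, without naming cycles. SAP 2 makes optional Cycle 3 lurbinectedin alone in both sequences. SAP 6.2 assigns end-of-treatment laboratory visits to the patient's last cycle.

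The PK analysis lies elsewhere: "The PK definitions and analysis plan will be described by the Clinical Pharmacology department in a separate document". That document was not available for this review.

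**The concern.** Myelosuppression is lurbinectedin's main known toxicity (Protocol 1.1), and Protocol 1.1.3.1 reports that neutropenia and its severity correlate strongly with AUC. Counts are therefore an informative safety measure if bosentan changes exposure. The crossover already supplies them in pairs: Protocol Table 5 schedules hematology on Days 8 and 15 of both Cycle 1 and Cycle 2. The by-treatment outputs reduce these pairs to grade categories, or to days in the subset of grade ≥3 cases. In 11.5 a neutrophil effect is also merged with any biochemical abnormality.

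The second issue is comparability. As written, one BOS+LRB cycle is set against up to two LRB-alone cycles. A worst-grade summary can only rise as cycles are added, so the extra exposure acts in one direction. The 11.5 model has a period term but does not say whether Cycle 3 is a third period.

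At stake is the precision and fairness of an exploratory safety comparison.

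**Working it through.** **1. The plan's own precision figure.** Protocol 9.2 and SAP 5.2 use 8 patients and an intra-subject CV of about 40%, and state a 90% CI half-width of 0.389 on the log scale. The formula is half-width = t(0.95, n−2) × SD × √(2/n). With n = 8 and SD = 0.40: 1.943 × 0.40 × 0.5 = 0.389. The figure is reproduced, so the same formula can be used for counts.

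**2. What a grade comparison can show with 8 pairs.** An exact two-sided sign test on patients who change category serves as a guide; the planned GLMM is not exact.

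- 6 of 6 in one direction: 2 × 0.5⁶ = 0.031
- 5 of 5: 2 × 0.5⁵ = 0.063
- 7 against 1: 2 × (1 + 8)/256 = 0.070

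So p<0.05 needs at least six changers, all the same way. Protocol 1.1.3.5 models 69% grade 3/4 neutropenia in the first cycle. That gives 8 × 0.69 = 5.5 expected cases and P(6 or more) = 0.53. Assuming independence within patient, the power of this test against a fall from 69% is 6% (to 35%), 17% (to 20%) and 32% (to 10%).

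**3. What a log-count comparison could show.** The documents give no within-patient SD for counts, so a range is assumed. Entries are the 90% CI factor for the Test/Reference ratio, exp(half-width).

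| Patients | t × √(2/n) | SD 0.30 | SD 0.45 | SD 0.60 |
|---|---|---|---|---|
| 8 | 1.943 × 0.500 | 1.34 | 1.55 | 1.79 |
| 6 | 2.132 × 0.577 | 1.45 | 1.74 | 2.09 |
| 4 | 2.920 × 0.707 | 1.86 | 2.53 | 3.45 |

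The rows for 6 and 4 show what remains if patients are excluded in a sensitivity analysis. With 8 patients, power for a two-fold count difference (two-sided 5%) is 97%, 85%, 55% or 38% for an assumed within-patient CV of 30%, 40%, 60% or 80%. This alternative is not matched to those in step 2, so the contrast is only indicative.

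**4. Cycle 3.** Reference carries no cycle limit, Cycle 3 is LRB alone in both sequences, and Table 11.4.1.1 takes the worst grade per treatment. Cycle 3 values therefore enter the LRB-alone column. Routine Cycle 3 hematology is taken on Day 1 before infusion (Protocol Table 5) and at end of treatment, 31 ± 10 days after the last dose (Protocol 6.5). No nadir draw is scheduled.

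**5. Days in Table 11.4.3.2.** Protocol 1.1 puts the nadir in the middle of the second week, between the two scheduled draws.

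- On schedule, a first grade ≥3 value reached on Day 9 is seen on Day 15, so it is dated 6 days late.
- With the ± 2-day windows, draws may fall on Days 6 and 17. An onset on Day 7 is then dated 10 days late.
- Days 11-12 lie outside both windows (Days 6-10 and 13-17).

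Where no unscheduled draw intervenes, onset and nadir days are sampled days, not true ones.

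**The case against.** The strongest reply is that Protocol 9.3.2 plans descriptive safety statistics, eight patients can be read line by line, and the SAP already lets a reader do so. SAP 6.2 promises worst grade per patient and per cycle, and Listing 11.4.1.5 gives grade ≥3 hematology by cycle. This stands in part: Cycle 3 events can be spotted and grades paired by hand. It does not correct the by-treatment columns or the 11.5 model, and it does not turn the counts into a comparison.

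Three stronger readings are tempting, and the documents do not support them.

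- *A reader might infer that the SAP compares grades and nothing else.* Table 11.4.3.2 compares days by treatment, although only for grade ≥3 cases, and 11.4.3 allows graphs.
- *A reader might infer that Cycle 3 badly inflates the LRB-alone column.* Two independent, fully sampled cycles would turn 69% into 1 − 0.31² = 90%. Cycle 3 is not fully sampled. Its Day 1 infusion requires ANC ≥1.5 × 10⁹/L and platelets ≥100 × 10⁹/L (Protocol Table 7), and the next routine draw is at end of treatment. Independence is also doubtful, because grade 4 neutropenia is a criterion for dose reduction (Protocol 7.5).
- *A reader might infer from the 48-72 hour recheck after Day 15 in Sequence 2 (Protocol 7.4) that recovery is sampled more closely under LRB alone.* For grade ≥3 abnormalities, Protocol Table 5 footnote b sets the retest interval by sequence, and Protocol 8.3 does the same for treatment-related grade ≥3 events. Neither has a cycle limit, so each patient keeps one interval under both treatments. Table 11.4.3.2 follows recovery only to grade ≤2.

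Limits on the count analysis also stand. Cycle 2 dose reductions and G-CSF affect counts. If the bosentan-cycle dose is adjusted to match AUC in the last five patients, their ratios are pushed towards 1. The unseen PK plan may already contain an exposure-count analysis.

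**Conclusion.** The point holds in a limited form. In this SAP, by-treatment comparisons of myelosuppression are grade-based or confined to grade ≥3 cases. Scheduled paired counts are not compared, and nothing restricts the LRB-alone column to Cycles 1-2. Including Cycle 3 can only raise that column's worst grade. The laboratory effect is probably small and cannot be quantified from the documents. The main loss is information: a grade cut-off needs six one-directional changes among eight patients, whereas a count ratio would have a usable, if wide, interval.

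The 69% is illustrative. It is modelled at a baseline ANC of 2.0 × 10⁹/L, which is this trial's entry minimum, so it is probably an upper figure here. The dose behind it is not stated with it. The count precision rests on assumed SDs, and the power figures for grades rest on independence within patient.

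This is a worthwhile, inexpensive improvement to an exploratory safety analysis, held with medium confidence.

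**What to change.** 1. Restrict Tables 11.4.1.1 and 11.4.3.2 and the laboratory rows of 11.5 to Cycles 1-2, and list Cycle 3 separately. In Table 11.4.3.2, label the rows as first sampled and lowest sampled day, and recovery as the sampled day.
2. Add one exploratory table of scheduled Day 8 and Day 15 ANC and platelet counts by treatment. For each count and day, give the Test/Reference ratio and 90% CI from the crossover model on log counts (treatment, period, sequence, patient within sequence), and show actual draw days. Flag G-CSF use and unequal lurbinectedin doses between the two cycles, and repeat the analysis without those patients.
3. If the separate PK plan already holds this comparison, cross-refer to it instead.

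The cost is SAP wording and one table from data already scheduled. The downside is four imprecise ratios from eight patients, with the mid-second-week nadir still unsampled. The sensitivity set may be too small to interpret: at four patients the interval is ×/÷ 1.86 to 3.45 over the assumed SDs.

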11.5 Linear Mixed-effects Model

If applicable, to compare the incidence of grade ≥ 4 or grade ≥ 3 between the combination and lurbinectedin alone, a generalized linear mixed-effects model will be fit to the data with treatment (Combination or lurbinectedin alone), period and sequence as fixed effects, and patients nested in sequences as a random effect.

Table 11.5.1.1 Safety comparison between combination and lurbinectedin alone[†]

	Combination	Lurbinectedin alone	p-value [‡]
Any grade ≥ 3 AE			
Any grade ≥ 4 AE			
Any grade ≥ 3 treatment-related AE			
Any grade ≥ 4 treatment-related AE			
Any abnormality (G ≥ 3) in laboratory value (hema, bio)			
Any abnormality (G ≥ 4) in laboratory value (hema, bio)			

[†] A generalized mixed-effects model will be fit for each safety evaluation

[‡] p-values will be provided for the comparison between treatments (combination vs. Lurbinectedin alone) or including the sequence effect if deemed necessary.

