1.1.3.1 Phase I Trials

Currently, this program comprises four single-agent studies, three in solid tumors (one ongoing in Japanese patients) ([Table 1](#)) and one in acute leukemia patients, six phase Ib combination studies with gemcitabine (GEM), capecitabine, doxorubicin (DOX), cisplatin, paclitaxel with or without bevacizumab (BEV), and irinotecan in patients with selected advanced solid tumors.

The First-in-Human (FiH) study (PM1183-A-001-08) was conducted in patients with advanced and refractory solid tumors and evaluated lurbinectedin intravenously (i.v.) infused over one hour every three weeks (q3wk). Thirty-three patients were included and thirty-one patients were treated. The recommended dose (RD) was established at an equivalent dose of 4.0 mg/m²/q3wk [\[13\]](#). Since lurbinectedin clearance was found to be unrelated to body surface area (BSA), all patients in the RD expansion cohort were treated at a flat dose (FD) of 7.0 mg q3wk (equivalent to 4 mg/m²). However, further

linear regression showed a strong correlation between neutropenia and its severity with the systemic exposure (area under the concentration-time curve – AUC), and for this reason, lurbinectedin prescriptions are currently calculated against BSA; moreover, phase Ib trials started with a FD and were amended to use a BSA-based dose. In this study (and subsequent studies), the median terminal plasma half-life ($T_{1/2}$) was around 60 hours, with a plasma clearance (CL) close to 12 L/h though large inter-individual variability exists. Urinary excretion of unaltered lurbinectedin was almost negligible regardless of dose; the mean percentage of unaltered drug recovered in urine at the recommended dose was 0.23% [13].

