2.2 SECONDARY OBJECTIVES

- To assess the effect of bosentan on lorbinecetin unbound plasma exposure.
- To assess the effect of bosentan on lorbinecetin major metabolites (i.e., M1 and M4).
- To assess the effect of bosentan on the safety profile of lorbinecetin.
- To collect and store a blood sample for germline DNA extraction for future pharmacogenetic (PGt) analysis of variations on genes that may influence exposure and response (i.e., disposition, metabolism and safety) to lorbinecetin.

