This study was designed to assess the potential effects of bosentan on the PK of lorbinecetin in patients with advanced malignancies. The 90% confidence interval (CI) will be used to help with the interpretation of the results. A sample size of eight patients was based on feasibility and clinical considerations. Based on previous studies, the intra-subject coefficient of variation (CV) of lorbinecetin PK parameters is estimated to be more than 30%. The precision (half-width) of the 90% CI for [(lorbinecetin + bosentan) / lorbinecetin alone] comparison on the log-scale will extend 0.389 from the observed differences in means, assuming that the intra-subject CV around 40%. This half-width corresponds to a 90% CI in the range of 70% and 147% assuming the ratio of the means equal to unity for each PK parameter. This 90% CI will be used to help with the interpretation of the results.

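### SAP 11.5 models laboratory safety only as a pooled yes/no flag with a p-value, which drops the size of any shift and the parameter it occurs in

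*SAP*

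**What the plan says.** A secondary objective in Protocol 2.2 is "To assess the effect of bosentan on the safety profile of" lurbinectedin. Safety data are otherwise summarized descriptively (Protocol 9.3.2, SAP 6).

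SAP 11.5 adds a model, to be used where applicable, "to compare the incidence of grade ≥ 4 or grade ≥ 3 between the combination and" lurbinectedin alone. It is a generalized linear mixed model with treatment, period and sequence as fixed effects and patient within sequence as a random effect. Table 11.5.1.1 has four adverse-event rows and two laboratory rows. The laboratory rows are yes/no flags for any abnormality at grade ≥3 and at grade ≥4, over hematology and biochemistry together. The columns are the two treatments and a p-value. There is no column for an odds ratio, a difference or an interval, and no test or significance level is named.

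Elsewhere the SAP tabulates worst grade by treatment for each cytopenia (Table 11.4.1.1) and each chemistry abnormality (Table 11.4.2.1), gives time courses of grade ≥3 events (Tables 11.4.3.2 and 11.4.3.4), and lists individual values (Listings 13.19 and 13.21). No model of the laboratory values themselves is planned.

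On size, SAP 5.2 states: "A sample size of eight patients was based on feasibility and clinical considerations". The precision it quotes is for pharmacokinetics (PK).

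**The concern.** The trial collects better data than this comparison uses. Protocol 6.4 (Table 5) schedules hematology and liver enzymes on Days 8 and 15 of both cycles, so each patient supplies paired continuous values. Protocol 1.1.3.1 reports a "strong correlation between neutropenia and its severity with the systemic exposure". If bosentan changes lurbinectedin exposure, blood counts should shift, yet a grade cut records only patients who cross it.

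Many may not cross. Protocol 1.1.3.5 estimates grade 3/4 neutropenia at about 69% in Cycle 1 for a baseline ANC of 2.0 × 10⁹/L, the eligibility floor. Pooling adds to this. If the flag covers the parameters of Table 11.4.2.1, one grade 3 GGT or glucose value sets it to yes, and opposite movements in counts and chemistry cancel or stay hidden.

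At stake is how the secondary objective is read. A non-significant p-value from eight patients, with no interval beside it, is easily taken as no effect.

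**Working it through.** **1. The plan's own figure.** With "assuming that the intra-subject CV around 40" percent, the SAP says the interval for the treatment "comparison on the log-scale will extend 0.389 from the observed differences in means". Check: t(0.95, 6 df) × SD × √(2/8) = 1.943 × 0.40 × 0.5 = 0.389, so it reproduces. (exp(±0.389) is 68% to 148%, so the stated lower limit of 70% is slightly off.) This is PK precision; no power is stated for any safety comparison.

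**2. What a paired yes/no test needs with eight patients.** An exact McNemar test gives p = 2 × 0.5⁶ = 0.031 for 6 of 6 discordant patients in one direction, 2 × 0.5⁵ = 0.0625 for 5 of 5, and 0.070 for 7 of 8. At least six discordant patients, all in one direction, are therefore needed. Even if bosentan abolished every event, power is P(Bin(8, p) ≥ 6): 53% at p = 0.69, 5% at p = 0.40 (the grade 4 neutropenia rate in Protocol 1.1.3.1, at that trial's recommended dose) and 0.01% at p = 0.13 (thrombocytopenia, Protocol 1.1.3.5).

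**3. The planned model against a continuous one.** Assumptions, none of them in the documents: a normal latent value cut at the reference rate, a stated correlation between a patient's two cycles, and two-sided 5%. The logistic mixed model of SAP 11.5 was fitted to all 1,225 possible outcomes for 4 + 4 patients, which gives exact power. The continuous comparator is the period-adjusted crossover t test on 6 df, with noncentrality shift/√(2/8). Reference rate 69%, correlation 0.5:

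| Shift (within-patient SD) | Continuous | Exact McNemar | Wald z | Wald t, 6 df | Likelihood ratio |
|---|---|---|---|---|---|
| 0 (size) | 5% | <0.1% | 1.1% | 0% | 7.9% |
| 1.0 | 39% | 1.7% | 6.6% | 0% | 37% |
| 1.5 | 71% | 6.9% | 8.9% | 0% | 63% |
| 2.0 | 91% | 17% | 7.1% | 0% | 82% |

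Over reference rates of 40%, 69% and 85%, correlations of 0.3 to 0.7 and shifts of 1 to 2 SD, power is 0.1% to 31% (McNemar), 0.1% to 11% (Wald z), 0% (Wald t) and 15% to 88% (likelihood ratio, true size 2% to 11%).

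**4. The same question in ANC terms.** Assumed: lognormal lowest ANC, total log-SD 0.8, within-patient log-SD 0.4 to 0.6, reference rate 40% to 69%. By simulation:

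| Ratio of lowest ANC | Crossover model on log value | Exact McNemar | Asymptotic McNemar |
|---|---|---|---|
| 1.5 | 20% to 40% | under 1% | 5% to 11% |
| 2.0 | 49% to 83% | 1% to 4% | 15% to 28% |

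At a ratio of 2.0, 56% to 71% of patients fall on the same side of the cut in both cycles. The type I error of the continuous model is 5%.

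**5. Information lost.** Write p10 for the probability of an event on reference only and p01 for an event on test only. The binary signal per patient is (p10 − p01)² / [p10 + p01 − (p10 − p01)²]; the continuous signal is shift²/2. For shifts of 0.5 to 1.5 SD the ratio of the two is 0.25 to 0.59, so 41% to 75% of the information on a single parameter is lost, before any pooling.

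**6. What the continuous analysis would deliver.** The 90% half-width is 1.943 × 0.4 × 0.5 = 0.389 to 1.943 × 0.6 × 0.5 = 0.583, that is, a ratio known to within a factor of about 1.5 to 1.8.

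**The case against.** Safety is descriptive in both documents, 11.5 is conditional, and the sample size was never justified by a safety comparison. Low power in an optional table contradicts nothing in the plan. That stands, and it limits the point to an improvement in an exploratory analysis.

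A reader might infer that ANC, platelets and transaminases are examined only in pooled form, or that pairing is thrown away. The documents support neither: each parameter is tabulated by treatment, and the random patient effect keeps the pairing.

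A reader might also infer that any test on the cut data is nearly powerless. In the step 3 table the likelihood-ratio test trails the continuous model by only 2 to 9 points. Its size there is 7.9%, however, and in other settings the gap is wider: at a 40% reference rate and correlation 0.5 it has 29%, 43% and 54%. The composite flag itself, platelets and transaminases were not simulated.

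Finally, a continuous analysis has its own weaknesses. Protocol 3.1 allows the lurbinectedin dose given with bosentan to change for the last five patients so that AUC matches, which could remove an exposure-driven shift. If only three of eight patients carried a ratio of 2.0, continuous power would fall from 49%–82% to 9%–12% (reference rate 69%); the binary rows would suffer too. Cycle 2 dose reductions (Protocol 7.5) and G-CSF also affect both. Days 8 and 15, each ±2 days, can miss a nadir that Protocol 1.1 places in the middle of the second week. These points shape the fix; they do not remove the need for an estimate with an interval.

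**Conclusion.** The point holds as a weakness of an exploratory secondary analysis. The only modelled laboratory comparison discards magnitude and parameter identity and returns a p-value without an effect estimate. Exact and Wald tests on the cut data have very low power for the shifts examined. A likelihood-ratio test has more, with a size that can exceed its nominal level, and the SAP does not say which applies. All power figures depend on assumed variability, correlation and effect, and the 69% is a model estimate at the lowest eligible ANC, not a typical rate. The case for change does not rest on power alone: a ratio with its interval shows what eight patients can and cannot exclude. The documents do not support the stronger conclusion that the safety objective goes unanswered.

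**What to change.** In SAP 11.5, add as the main modelled laboratory comparison a crossover mixed model with treatment, period and sequence fixed and patient within sequence random, the form Protocol 9.3.4 already uses for PK. Fit it to log lowest scheduled Day 8/15 ANC and platelets and log highest scheduled Day 8/15 ALT and AST (× ULN), using Cycles 1 and 2 only, so that the optional third cycle gives lurbinectedin alone no extra opportunity for events. Report Test/Reference ratios with 90% CIs.

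Label these results and any pooled binary p-values exploratory, and keep Tables 11.4.1.1 and 11.4.2.1. State that the values are not dose-normalized. Flag patients whose lurbinectedin dose differed between cycles or who received G-CSF, and add a sensitivity run for them.

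The cost is SAP text and a few more model runs. The estimates will remain imprecise at n = 8, and the scheduled samples may miss the true nadir.
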